## POWER AND SAMPLE SIZE CALCULATION

### **Sampling**

During revision, we reversed our changes for the selection criteria following reviewers' suggestion to refocus our efforts on Veterans with mild TBI. The TBI clinic is held on a daily basis at the DC VAMC. This clinic evaluates 150-200 new Veterans per year who are identified with a positive TBI screen. Currently, the positive TBI diagnosis rate is approximately 50% for the DC VAMC site. In addition, other Veterans with known TBI are referred to the clinic resulting in additional 50-100 referrals per year. Frequency of follow-up visits is determined on an individualized basis. In addition to the Veterans with TBI who are hospitalized at the DC VAMC each year, many Veterans seen at the Richmond Polytrauma Rehab Center and discharged to the Washington DC Metro area are then seen in the DC VAMC TBI clinic. Everyone who consents to the study will be examined using the FrSBe. It is estimated that 50-75% of Veterans with mild TBI, have impaired decision-making/executive dysfunction and will be eligible and willing to participate in the study.

### **Power and sample size calculation**

110 participants with executive dysfunction due to diagnosed TBI will be randomized into the COMPASSgoal intervention or supported discharge groups, as assessed via the VHA TBI Comprehensive Evaluation screening tool. Participants in the supported discharge group will not receive the intervention, but will receive usual care provided by case managers with increased intensity of communication prompts. Participants in the intervention group will receive 8 goal self-management sessions over a period of approximately 10 weeks. We don't expect a significant change from post-intervention to 3 month post-intervention, the sample size calculations are based on a t-test for comparisons of mean change in the Community Reintegration of Service members (CRIS) subscale from pre- to post-intervention between two groups.

### **Hypothesis:**

H0:  $\mu_1 = \mu_2$  where  $\mu_1$ = mean change in CRIS subscale from time 1 to time 2 in self-management group and  $\mu_2$ = mean change in CRIS subscale from time 1 to time 2 in supported discharge group  
H1:  $\mu_1 \neq \mu_2$

**Power Calculation:** PASS (Power Analysis and Sample Size Software, Kaysville, UT, 2008) was used for the power calculation. The primary outcome of this study is the frequency of social interactions measured via the Extent of Participation subscale of the CRIS. The power calculation was performed based on the hypothesis listed above by using a two-sided t-test with assumption of normality. The level of significance was set at 0.05 and power was set at 90%. The effect size and standard deviation used for the power calculation were estimated based on a previous VA study and clinical judgment. 44 subjects in each

[figure not shown]
group, for a total of 88 subjects will provide 90% power to test an effect size of 0.71 with a SD of 7 for difference in CRIS subscale score between groups with  $\alpha=0.05$  (two sided). After adjustment for 20% loss to follow-up, we will recruit 55 subjects in each group of this study, a total of 110 subjects.

## COMPASS PROCEDURES AND IMPLEMENTATIONS

Study procedures will take place at the DC VAMC in Washington, DC either face-to-face or over the VA Telehealth System (see Study Algorithm, Figure 5). All research procedures, including assessments, may be completed over the phone, not including informed consent. Over the 3-year course of the COMPASSgoal project, we will screen, consent, and baseline 110 Veterans, aged 18-55 years, who have been diagnosed with MTBI. All participating Veterans will undergo a battery of tests measuring executive function, real-world performance, TBI self-efficacy, emotional status and PTSD resilience, community integration, and quality of life. Each will receive additional screening of TBI and executive dysfunction to determine intervention eligibility. COMPASSgoal investigators will discuss each participating Veteran with his/her VA case manager.

Subsequently, Veterans will be randomized to intervention and control groups. The former will receive the COMPASSgoal self-management intervention developed to support vulnerable transitions identified during the first 6 months of the project. The latter will receive focused, but standard-of-care, support from the VA TBI Clinic team. Intervention group Veterans will receive 8, weekly, up to 90-minutes, one-on-one goal management sessions over a period of 2 months. Goal sessions with coaches, as well as control group interactions and assessments, will be audio recorded to better inform the researchers about the effectiveness of the interventions. These sessions may occur in person or over the phone. Veterans in both the intervention and control groups will receive assessments pre-, post-, and 3 months following completion of the COMPASSgoal intervention or supported discharge process. Data will be modeled longitudinally and on multiple levels to identify vulnerable transitions and predictors of community integration/participation outcomes.

Findings will form the basis for clinical practice guidelines.

**Figure 5. COMPASS Study Algorithm**

## Recruitment Process

Participants will be recruited from DC VAMC by [name] (PI), [name] (Co-PI; Polytrauma Clinic Director, and their clinical associates. Consecutive patients approaching discharge from multi-disciplinary care who meet the inclusion/exclusion criteria will be notified of the study and approached for informed consent. If necessary, participants will be recruited using recruitment flyers. Following consent procedures, individuals agreeing to participate in the study will be asked a series of screening questions to ensure that they have met all inclusion/exclusion criteria. In addition, study investigators will take special precautions to ensure that potential study participants fully understand the consent form and authorization for the release of Protected Health Information (e.g., by reviewing the consent form and answering any questions the individual may have - see details in the Human Subjects section).

### ***Screening for exclusion-inclusion criteria***

Potential participants will be approached at least three months after TBI for informed consent. The results of the **VHA TBI Comprehensive Evaluation electronic template** will be reviewed following IRB approved and HIPAA compliant data collection procedures. The first data collection will take place within the first 14 days after screening and enrollment into the project.

### ***Informed Consent Process***

Upon identifying a potential subject in the DC VAMC TBI database or through the TBI Case Manager, the study PI and Co-PI ([name]) or treating physician will speak with the TBI patient and family, as appropriate to each Veteran's circumstances, about the study. In addition, the treating physician will introduce the research team to the families of patients. Special care will be taken to explain the nature of the study and all risks/benefits to the individual in language that is appropriate for his/her comprehension level. Once written consent has been obtained, subjects will be assigned a de-identified study number for data collection purposes by the PI.

### ***Testing setting***

For both standard and computerized testing, participants will be provided with a quiet room, a desk, and a chair. We will make every effort to standardize testing conditions. Assessments will be audio recorded for quality control purposes.

### ***Patient retention and PI prior recruiting experiences***

Based on the PI's prior experiences, we are confident in the success of study recruitment and retention procedures. In addition, we will be using a motivational technique that previously proved to be very useful in participant recruitment and retention. An IRB approved Certificate of Participation (Thank You letter) template will be used to provide participants and family members with appreciation for participation in the study in comprehensible, "layman" language. This will not only keep participants engaged with the study, but will also potentially create a study atmosphere that will motivate them to bring other potential participants to the study to benefit from the same experience.

To encourage ongoing patient engagement between assessment sessions T2 and T3, Veterans will receive IRB-approved Engagement Templates as reminders of COMPASS participation. This will remind participants that they are enrolled in the COMPASS study without providing information that may influence study variables. Further, participants who initially engaged with the study team, but are lost to follow-up will also receive an IRB-approved Follow-up Letter asking them to contact the study team to confirm continued participation in the study. See Appendix 4 for the letter templates.

### ***Overall rationale for the assessment model***

While assembling the study assessment battery we considered the following rules: a) relevance of the proposed measure to the study Specific Aim and Hypotheses; b) the balance of the proposed measures by

modes of expression and assessment quality (self-reported assessment vs. experimental technique vs. observation by a clinician or a family member); c) the possibility of premorbid executive functioning evaluation and sequential charting of executive function over time as it returns to the estimate; and d) possibility of linking performance at the baseline with executive performance over time, using reliable change models to determine if the change meets criteria for some a priori "recovery threshold".

Included in Table 2 below and Appendix 1 (*Assessment Schedule*), core TBI measures were suggested by the TBI Common Data Elements work group and/or were used in community integration TBI studies while implementing a multilevel approach to data analysis. **The National Institute of Neurological Disorders and Stroke (NINDS), the Department of Veterans Affairs (VA), the National Institute on Disability and Rehabilitation Research (NIDRR), the Defense Centers of Excellence for Psychological Health and Traumatic Brain Injury (DCoE), and the Defense and Veterans Brain Injury Center (DVBIC) have co-sponsored this scientific initiative to develop common data elements (CDEs) for TBI research.**

In accordance with the study Specific Aim, we also considered psychosocial individual assessments that capture the subjective aspects of recovery including resilience, amount of stress (PTSD), functional capacity, emotional status (including depression and anxiety levels), TBI self-efficacy, coping, and life satisfaction. These measures have proved external validity and are commonly used in TBI studies (see Table 2, *Assessment Schedule*). The behavioral assessment focuses on individual performance of real-world tasks. The community integration measures focus on different aspects of societal participation and individual productivity including educational attainment and employment. These measures also have good construct validity, test-retest reliability, and importantly, they are sensitive to change. Most measures employ alternate forms or demonstrate low practice effect which makes them appropriate for repeated administration. We are also aware that the types of measures included are complementary such that "recovery" on the objective measures might not reflect "recovery" on the subjective measures.

## STUDY ASSESSMENT SCHEDULE

Assessments will be performed at baseline (termed as "pre-intervention" for the COMPASSgoal group), 2 months (or post-intervention for the intervention group), and 3 months follow up for both intervention and supported discharge groups. Participants involved with the COMPASSgoal intervention (see relevant section below) will receive 8 goal self-management sessions over a 2-month period. The data will include demographics, level of TBI severity as confirmed by duration of post-traumatic amnesia and alteration of consciousness based on the VHA TBI Comprehensive Evaluation screening tool, executive dysfunction, PTSD, resilience, emotional status, coping, TBI self-efficacy, real-world tasks, and community integration. Family members will be invited to participate and answer the family-report FrSBe assessment either in person or over the telephone after being contacted through an IRB-approved letter.

**Table 2: Multifactorial Executive Functioning, Psychological, Behavioral, and Community Integration Measures (for a detailed description see Appendix 1, *Assessment Schedule*)**  
**NOTE. Table 2 was significantly revised; therefore changes are not italicized.**

Domain	Test	Description	Study Protocol	Time
Cognitive functioning and TBI severity	TBI screening (VHA TBI Comprehensive Evaluation screening tool)	Reliable measure for detecting cognitive impairment in service members. If the Veteran does not have a CTBIE available in the medical record, questions 6-8 will be collected by an IRB-	Screening for exclusion	*

Domain	Test	Description	Study Protocol	Time
		approved member of the Polytrauma team.		
Executive dysfunction	FrSBe ** 80, 82	Frontal systems Behavioral Scale, 46-items. Both self-report and Family-report.	Executive dysfunction due to TBI	10 min
Demographic Information	Patient Information Form	8 questions about demographics	Collected once during exclusionary screening	5 minutes
Mental Health	MINI International Neuropsychiatric Interview (MINI) 7.0.0^68	Reliable measure of Mental Disorders from DSM-V, including depression, suicidal ideation, manic and hypomanic episodes, panic disorder, agoraphobia, social phobia, obsessive-compulsive disorder, post traumatic stress disorder, alcohol dependence/abuse, substance dependence/abuse, psychotic and mood disorders, anorexia nervosa, bulimia nervosa, generalized anxiety disorder, and antisocial personality disorder.	Determination of mental health disorders in absence of clinical judgment within past year.	15 min
Executive dysfunction	TMT Trail Making Test	Trail Making Test (Part A and B) This is a measure of cognitive processing speed, mental sequencing, visual search and motor speed and consists of two components: Part A and Part B. Part A requires the subject to connect 15 encircled numbers that are randomly arranged on a page in numerical order. Part B requires	Executive dysfunction due to TBI	5 min

Domain	Test	Description	Study Protocol	Time
		the subject to connect 15 encircled numbers and letters in alternating order. The score provided is time required to complete the task.		
Executive dysfunction	COWAT Controlled Oral Word Association Test	Controlled Oral Word Association Test (COWAT) This is a measure of word generation and is considered an executive functioning measure. Letter Fluency requires the person to generate words that start with a specific letter. Category Fluency requires generation of words from within a specific category (e.g., animals). Each trial lasts for one minute and the score is based on the number of words provided.	Executive dysfunction due to TBI	5 min
TBI Self-efficacy	TBI Self-efficacy Questionnaire	15-item TBI-specific scale of self-efficacy with regard to trauma	Measure of individual abilities to manage TBI consequences	5 min
Emotional status and resilience	BSI-18 assessment	Paper-and-pencil scale that consists of 18 items; 5-point rating scale and is part of the Common Data Elements set	Measures depression, anxiety, somatic concerns, and general distress	5 min
	Post-traumatic Stress Disorder Checklist (PCL)	Presence of PTSD symptoms. PCL is a 20 item self-report scale, updated for DSM-V.	Stress signs: intrusive thoughts, avoidance behavior, arousal symptoms	5 min
	Community Reintegration for Service Members	107 – items assessing Extent of Participation, Perceived Limitation in	Veteran-specific measure utilizing 3 unidimensional	25 mins

Domain	Test	Description	Study Protocol	Time
	(CRIS, Fixed Form; Resnik L.) 81, 82, 83, 84**	Participation, and Participation Satisfaction	scales	
	Social participation via ICF qualifiers: return to work and/or to school as defined by the ICF framework	Work status/educational attainment confirmed by a family member/immediate caregiver or other reliable source.	Categorical variables	*

\*Tests performed by attending clinician or as part of the routine care at the DC VAMC

\*\* If patients participate in the recruitment assessment within 1 month of participating in clinical trial, the test will not be repeated.

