In addition to the modifications described above, we will conduct a recruitment assessment prior to implementing the intervention. This portion of the study will not be audio recorded. The assessment will be part of routine clinical treatment and participation is mainly a release of records. In this assessment, we will document the approximate number (and thus, proportions) of new patients presenting for clinic services (without keeping personal identifiers associated with those data). Among this consecutive series of new patients, we will use an informed consent process to invite participation in a single, brief testing session, for those who screen positive for mild TBI, but do not have documented serious mental health co-morbidity (e.g., schizophrenia, major depressive disorder, clinically significant PTSD). Thus, these latter participants will grossly resemble those who might be invited into the COMPASS trial on discharge from rehabilitation team

treatment. Following informed consent, these participants will be given the main measure used for inclusion in the intervention study, the FrSBe, the primary outcome measure, the CRIS, and a short interview. Total participation is expected to take no more than 30 minutes and may be done either in person or by phone at the convenience of the Veteran (these 2 modes of administration have been shown to be psychometrically equivalent. In addition to consenting to answering the questions on these 2 measures, participants will be asked to consent to have their routine clinical data (age, gender, presenting symptoms, severity of TBI, records from the current episode of treatment) used as needed to correlate with the psychometric findings (without personal identifiers attached).

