The CRIS, our primary outcome measure, is equally important to assess in this sample in order to address the following objectives: (1) Determine the time needed to administer the measure, which is quite lengthy. Recently, the CRIS was converted to a computer-adapted (CAT) version which may substantially reduce participant burden. Before starting the assessment, we will contact the primary author of the measure to determine if the CAT and/ or validated short forms are available; (2) Verify that this measure, too, is sensitive to the community integration problems experienced by those with *mild* TBI. The CRIS has been validated thus far on Veterans with severe, mixed type injuries; homeless Veterans; and those with mental health diagnoses such as depression and PTSD, but not in our target population; (3) Derive preliminary data on the relationship, if any, between the FrSBe and the CRIS measures. Reid-Arndt et al. (2007) found that the FrSBe predicted community integration only weakly. However, that study used the Community Integration Questionnaire, a measure with known psychometric difficulties.

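### Table 2 lets the time-1 CRIS, the primary outcome, be carried over from a recruitment assessment up to a month old, so baseline timing, clinical stage and possibly form differ between participants; the cost is precision and interpretability, not between-arm bias

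*Combined protocol and SAP*

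**What the plan says.** In Table 2 (Study Assessment Schedule) the double-asterisk marker stands on two rows, the FrSBe and the CRIS Fixed Form of 107 items. The footnote reads: "If patients participate in the recruitment assessment within 1 month of participating in clinical trial, the test will not be repeated".

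The recruitment assessment is described under Goal Self-Management Intervention Development. On timing: "we will conduct a recruitment assessment prior to implementing the intervention". On who is tested: "Among this consecutive series of new patients, we will use an informed consent process to invite participation in a single, brief testing session". On content: "these participants will be given the main measure used for inclusion in the intervention study, the FrSBe, the primary outcome measure, the CRIS", followed by a short interview, all within 30 minutes. On the CRIS version, the team will ask its author to "determine if the CAT and/ or validated short forms are available".

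The trial has a different entry point. Under Recruitment Process: "Consecutive patients approaching discharge from multi-disciplinary care who meet the inclusion/exclusion criteria will be notified of the study". Under Screening for exclusion-inclusion criteria: "The first data collection will take place within the first 14 days after screening and enrollment into the project". Randomization follows collection of all baseline data.

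The sample-size section names the Extent of Participation subscale of the CRIS as the primary outcome and compares mean change from time 1 to time 2 between arms. The Statistical Analysis Plan has no rule for identifying, dating, adjusting for or excluding a carried-over baseline.

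**The concern.** A participant covered by the footnote has a time-1 value of the primary endpoint that was not taken at the trial baseline. It can differ from a fresh baseline in three respects.

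- **Timing.** The score may be a month old at trial entry, and the footnote does not say whether entry means consent, randomization or first session. This does not sit easily with first data collection within 14 days after enrollment.
- **Clinical stage.** The score comes from a new patient presenting to the clinic, while other baselines come from patients near the end of team care.
- **Form.** A computer-adaptive or short form is left open for the recruitment assessment, but the trial uses the Fixed Form. No bridging rule is given.

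Self-efficacy, BSI-18 and PCL do not carry the marker and are measured fresh. Only the primary outcome and the FrSBe, the MANCOVA covariate, can be old. At stake are a common meaning for the primary change score, the accuracy of reported within-arm change, and some power.

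**Working it through.** **The plan's own figure.** Inputs from the power section: standardized effect 0.71, SD 7 (a difference of 0.71 × 7 = 4.97 points), two-sided alpha 0.05, power 90%, 44 per group. The t-test calculation needs 42.7, so 43 per group; at 44 per group, power is 0.909. Allowing for 20% loss, 44 / 0.80 = 55 per group, 110 in total. The plan's figure reproduces, and no error in it is alleged.

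**Length of the interval.** The nominal change interval is 2 months. A score one month older makes it up to 3 months. If the month runs back from enrollment and the rest of the battery is taken 14 days after it, the CRIS could be about six weeks older than the other baseline measures.

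**Form.** Table 2 allots 10 minutes to the FrSBe and 25 to the CRIS Fixed Form: 10 + 25 = 35 minutes before any interview. The recruitment session is expected to take no more than 30. A shorter CRIS version there is therefore a live possibility, though the documents do not say that one was adopted.

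**Precision of the unadjusted change score.** The documents give neither the CRIS pre-post correlation nor the share carried over. Assumptions:

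- correlation 0.70 with a fresh baseline, and 0.65 or 0.60 with a carried one;
- mean shift during the gap of 0 to 5 points;
- share affected p of 2, 5, 10 or 25%;
- the same spread for carried and fresh scores.

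Change variance is proportional to 2(1 − correlation), so inflation in those affected is 0.35/0.30 = 1.17 or 0.40/0.30 = 1.33. Overall:

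variance = 49 × [(1 − p) + p × inflation] + p(1 − p) × shift²

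Worst case shown (p = 0.25, correlation 0.60, shift 5): 49 × (0.75 + 0.25 × 1.333) + 0.1875 × 25 = 53.08 + 4.69 = 57.77, so SD 7.60.

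| Share affected | SD of change | Power at 44 per arm |
|---|---|---|
| none | 7.00 | 0.909 |
| 2% | 7.01 to 7.06 | 0.908 to 0.904 |
| 5% | 7.03 to 7.14 | 0.906 to 0.898 |
| 10% | 7.06 to 7.27 | 0.904 to 0.887 |
| 25% | 7.14 to 7.60 | 0.897 to 0.858 |

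**With baseline as covariate**, as the Hypothesis 1 mixed models plan. A change SD of 7 and correlation 0.70 imply a single-occasion variance of 49 / (2 × 0.30) = 81.67. With fresh baselines the residual variance is 81.67 × (1 − 0.70²) = 41.65, SD 6.45, power 0.946. In the worst case above:

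- covariance of baseline and outcome = 81.67 × (0.75 × 0.70 + 0.25 × 0.60) = 55.13;
- baseline variance = 81.67 + 4.69 = 86.35;
- residual variance = 81.67 − 55.13² / 86.35 = 46.5, SD 6.82, power 0.922.

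**Between-arm bias.** The carried score is fixed before randomization, so its share and shift are balanced in expectation. A chance imbalance of 10 percentage points with a shift of 2 to 5 points would move the difference in mean change by 0.2 to 0.5 points, against a target of 4.97.

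**The case against.** The strongest reply is that hardly anyone will meet the footnote. The recruitment assessment comes before the intervention is implemented and tests new patients, excluding those with documented serious mental health comorbidity. To qualify, a new patient must come near discharge and enter the trial within a month. The text presents these people as resembling future participants, not as the source of them. Someone with at most a month of team care is also unlikely to have shifted by 5 points, which is the whole target effect. The footnote spares participants a lengthy questionnaire, and the 14-day rule can be read as a general rule to which the footnote is a specific exception. Most of this stands: it limits the size of the problem. It does not remove the lack of any rule for handling these scores.

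Two stronger readings should be resisted.

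- A reader might infer that power falls mostly below the planned 90%. That follows only from assuming a sizeable affected share together with a mean shift or a marked loss of correlation, and from ignoring the planned baseline adjustment. The documents support none of those inputs.
- A reader might infer from "used as needed to correlate with the psychometric findings (without personal identifiers attached" that recruitment scores cannot be linked to individuals, leaving the baseline missing. That phrase concerns consent to use routine clinical data in correlations, which itself needs person-level linkage. Participants consent, and the protocol provides for coded study numbers. Linkage could be stated more clearly, but the text does not show it to be impossible.

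**Conclusion.** The point holds as a modest, easily removed weakness in how the primary baseline is defined. The footnote does cover the CRIS, the recruitment assessment reaches patients at a different clinical stage, the form used there is not fixed, and the analysis plan is silent on carried-over values. The footnote and the 14-day rule need reconciling whatever the effect on power.

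The between-arm contrast is not biased. The harm is an uneven change interval, possibly uneven forms, within-arm change that may include change during clinic care, and some loss of precision. With 2 to 5% affected, unadjusted power is about 0.90 to 0.91; with 25%, 0.86 to 0.90; with baseline adjustment it is at least 0.92 even in the worst case examined. These ranges rest on the assumed correlations, shifts and shares, none of which the documents give.

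**What to change.** - Limit the Table 2 footnote to the FrSBe.
- Administer the CRIS Fixed Form to every participant at the trial baseline, before randomization, and define time 1 as that value only.
- For anyone already enrolled with a carried-over CRIS, record its date and form, and add a sensitivity analysis that excludes those baselines.

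The cost is about 25 minutes of participant time (the Table 2 allotment) for the subset who had the recruitment assessment within the month. It can be done by telephone, which the protocol already allows for assessments. The sample size stays at 44 evaluable and 55 recruited per group.
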